UNIVERSIDADE DA CORUÑA

Grupo de Investigación en Gerontología y Geriatría

Study Protocol and Statistical Analysis Plan

Protocol Official Title: **Low-volume Cycling Training Improves Body Composition and Functionality in Older People With Multimorbidity: a randomized controlled trial**

ClinicalTrials.gov ID: [Not yet assigned]

Date: 6th April 2021

Grupo de Investigación en Gerontología y Geriatría ©
Universidad de A Coruña

INTRODUCTION

Aging is a risk factor for most chronic diseases, and the presence of more than two diseases (i.e., multimorbidity), which is frequent in almost two out of three older adults, has been related to an increased risk of disability and frailty, a decrease in quality of life, and mortality (Pedersen, 2019). Physical activity (PA) acts as a nonpharmacological intervention and regular physical activity (rPA) reduces rates of all-cause mortality, compresses morbidity, decreases healthcare costs, and has relatively minimal adverse effects compared to drugs (Fiuza-Luces et al., 2013).

It has been estimated that 27.5% of the world's population in 2016 did not meet the recommendations established for the member states of the World Health Organization (WHO) for health-enhancing physical activity. Furthermore, recent studies showed that moderate-intensity physical activity may be sufficient for reducing the risk of all-cause dementia and that some of the protective benefits of physical activity for older adults (Cunningham et al., 2020). It seems indispensable to study adequate doses of exercise for older people who often have low levels of physical activity and fitness, who spend a large amount of time sitting down, and whose multimorbidity keeps them away from exercising.

OBJECTIVES

To study the effects of perception-regulated low-volume and low-to moderate intensity training on body composition, hemodynamic parameters, and functional performance in older adults with multimorbidity.

MATERIAL AND METHODS

Study design

This longitudinal and prospective study conducted between September and December 2019, is a 2 x 2 randomized controlled trial using a two-group design (exercise vs. control) and two repeated measures (pre- vs. postintervention). This study is performed following the CONSORT (CONsolidated Standards of Reporting Trials) 2010 guideline.

Study setting and participants

Participants are recruited between September and October 2019 at the Gerontological Complex La Milagrosa (A Coruña, Spain), consisting of a daycare center and a nursing home.

Inclusion criteria: (a) men and women aged 65 and older, (b) users of a care setting—daycare patients or nursing home residents, and (c) a score < 5 in the Global Deterioration Scale (GDS; Reisberg et al., 1982), from no cognitive decline to moderate cognitive decline.

Exclusion criteria: (a) physical limitations or musculoskeletal injuries that could affect cycling training performance; physical exercise contraindicated by the physiotherapist and verified by the medical doctor according to the medical register of each participant; (b) heart failure with a functional class according to the New York Heart Association (NYHA) Classification of NYHA III and IV; (c) the presence of acute pain that does not allow exercise training; (d) recent acute

myocardial infarction (in last 6 months) or unstable angina; (e) uncontrolled hypotension; (f) uncontrolled arterial hypertension ($>180/100$ mmHg); (g) active cancer treatment with chemotherapy; (h) patients with an active pacemaker and/or uncontrolled block; (i) diabetes mellitus with acute decompensation or uncontrolled hypoglycemia; or (j) any other circumstance that precludes individuals from completing the training intervention.

24 participants will be recruited and randomly placed into two groups: the exercise group (EG, n=12) and the control group (CG, n=12). A stratified permuted block randomization is employed that accounted for the GDS score, sex, and type of institutionalization. A nurse and a medical doctor enrolled and assigned participants to intervention.

Intervention

Cycloergometers

The Gerontological Complex La Milagrosa features a kinesiotherapy room equipped with three MOTOMed®muvi cycle ergometers (Fig. 1) adapted for older people. These cycle ergometers have the ability, through electric motors, to provide resistance to oppose cycling and, on the other hand, to passively move the limbs of the trainees. This movement system allows even subjects with loss of functional ability to mobilize (bipedestation or walking) to perform the activity from their wheelchair or geriatric chair.

Through the machines, the subjects can simultaneously activate more than 80% of the muscles of the body, because the device allows the execution of the activity, both for the upper and lower limbs. The MOTOMed®muvi allows you to control through your records the parameters: distance (Km), speed (m/s), duration (min), resistance (load), caloric consumption (Kcal), work done (J), and symmetry members' contralateral (%) (Fig. 2).

Figure 1

Figure 2. MOTOMed ®muvi' Screen

Familiarization

Participants familiarized themselves with the activities over 2 days of 4 to 16 minutes of simultaneous upper and lower limb cycling at a comfortable pace, progressing until volitional

stop. Older adults cycled on a recumbent motorized cycle (MOTomed® Muvi Movement Therapy Trainer; Reck-Technik GmbH & Co., Betzenweiler, Germany). The MOTomed Muvi has a display where velocity (m/s) and resistance (kg) can be observed when cycling; thus, within the familiarization session, researchers annotated the velocities employed for the participants cycling 2 minutes with 1 kg and encouraged them to maintain this cadence when the load was increased at a rate of 2 kg each 2-minute stage. The trial was terminated when the participant voluntarily stopped exercise owing to fatigue or discomfort. Furthermore, the trial was finished when the investigator determined that the participant could not maintain the designated pedaling rate for more than 10 consecutive seconds at the current load.

Before they began cycling, participants were anchored to the perception scale using a combination of exercise and memory procedures. This procedure required the participant to cognitively establish a perceived intensity of effort that is consonant with that depicted visually by a cyclist figure at the bottom (i.e., low anchor, rating 0) and top (i.e., high anchor, rating 10) of the hill, as presented in the OMNI-RPE scale illustrations [40]. The OMNI-RPE scale was visible at all times of the progressively increased resistance cycling exercise, and participants indicated a number before starting cycling and in the last 15 seconds of each stage. The familiarization period was conceived to train participants to anchor a score on the OMNI-RPE against a spectrum of intensities, defined by resistance applied, ensuring that they stop voluntarily at least once due to an inability to maintain the cadence set or a symptom-related alert (i.e., leg tightness/pain, dizziness, chest tightness/pain) that prevented them from exercising safely.

Intervention

The exercise group is requested to accomplish 18 sessions on the MOTomed Muvi, a low volume (i.e., 20 minutes per session, 3 days per week) and low-to-moderate intensity combining upper and lower limb recumbent cycling training for six weeks at an intensity guided by the perception of effort.

The interventions are divided into three stages, 10 minutes of activity, 5 minutes of rest, and again 10 minutes of activity. The exercise performed consists of raising the resistance (load) adapted to each subject, starting with a resistance of 5KJ, increasing from 5KJ by 5KJ to a maximum of 20KJ. The speed of exercise is set subjectively, i.e. each patient manages and maintains the speed with which they feel most comfortable so that they can end the total time of each training session. In any case, and to prevent the cycle ergometer from passively boosting the upper or lower limbs, a basal (minimum) speed of 15 rpm is set. So, participants are informed and encouraged to increase their speed of movement above the minimum threshold. Besides, and to maintain a minimum control of rotations per minute and the machine presenting an isopotential mechanism (automatic adjustment of power according to speed and resistance) states that patients should not exceed a speed of 30rpm.

Therefore, a cycling cadence is fixed between 25 and 30 rpm for all sessions since that cadence is comfortable for every participant. Researchers adjust the resistance on the motorized cycle to increase the external load until it reached the level required to reach the intensity of effort programmed by the OMNI-RPE (Guidetti et al., 2011). The six weeks are programmed in the form of two intensity- differentiated training phases of three weeks. In the first training phase (i.e., the first three weeks), participants are requested to cycle simultaneously with the upper and

lower limbs at an intensity equivalent to a perception of 3 (i.e., easy to somewhat moderate) on the OMNI-RPE (0-10).

Control of adverse events was measured through the assessment and monitoring of vital signs before, during (within the first 10 minutes), and after the intervention sessions. Vital signs [heart rate (per minute), systolic and diastolic blood pressure (in millimeters of mercury, mm Hg), and oxygen saturation (in percentage)] were monitored by a nurse and a medical doctor using mobile finger pulse oximeters.

Throughout the training, evaluators are responsible for postural control and patient symmetry parameters controlled through the cycle ergometer screen.

The body posture of the participants in the chair in front of the machine is controlled considering the measurements of the appropriate joint angles in the knee, through a rule of ergometry. Two types of chairs are used for the performance of the activity, one conventional chair, and a geriatric chair in case the patient needs it to move.

For sitting, conventional geriatric chairs are used, seeking to respect the angles of the knee joint corresponding to a 152° extension, a 110° flexion, and a Range of Movement (ROM) of 42°. For the geriatric armchair, the values are extension 144°, flexion 105°, and ROM 39°.

Finally, it is established as a final criterion to consider the participant to complete at least 80% of the scheduled sessions (14 out of 18 sessions).

Participants (experimental and control group) are evaluated to examine the changes in body composition, functional performance, and resting cardiovascular state. Furthermore, participants are monitored physiologically during each session (heart rate and blood pressure) to control any possible adverse effects.

Measures

Pre- and post-intervention assessments are made on all subjects of the sample (control and experimental group). Pre-intervention data were collected one week before the start of training, while post-intervention data were recorded at the end, after six weeks of intervention.

Socio-demographic variables

Age (years) and gender.

Body composition evaluation

Bioimpedance analysis (Inbody 270): body weight (kg), height (cm), muscle mass (MM), fat mass (FM), and FM percentage. Waist circumference (WC, cm) is taken at end-tidal using a measuring tape to the nearest 0.1 cm, midway between the lowest rib and the iliac crest, which corresponded with the level of the umbilicus. Body mass index (BMI) is established by the Quetelet index: $BMI \text{ (kg/m}^2\text{)} = \text{mass (kg)} / \text{height (m)}^2$.

Figure 3. InBody 270

Hemodynamic parameter evaluation

The baseline hemodynamic state is characterized by storing the mean of the three lowest values for thirty seconds of heart rate (HRrest, mm Hg) and oxygen saturation with a finger pulse oximeter; blood pressure by the auscultator method using a properly calibrated mercury column sphygmomanometer flexible cuff of the appropriate size and a stethoscope; three systolic (SBPrest) and diastolic blood pressure (DBPrest) measurements are recorded at 1-minute intervals. Mean blood pressure (MBPrest) is calculated as follows:

$$\text{MBP} = \text{DBP} + 1/3 (\text{SBP} - \text{DBP}).$$

Functional evaluation

- a) Frailty. Assessed by Fried et al. (2001), based on the presence or absence of 5 specific and phenotypic components (1) unintentional weight loss: at least 4.5 kg in the past year; (2) self-reported exhaustion, identified by 2 questions from the modified 10-item Center for Epidemiological Studies-Depression scale; (3) weakness: grip strength in the lowest 20% at baseline, adjusted for sex and body mass index; (4) slow walking speed: the slowest 20% at baseline, based on time to walk 4.6 m, adjusting for sex and standing height; and (5) low physical activity: the lowest 20% at baseline, based on a weighted score of kilocalories expended per week.
- b) The Performance-Oriented Mobility Assessment (i.e., POMA; Tinetti, 1986), which measures balance (i.e., POMA-B) and gait performance (i.e., POMA-G) and the total score (i.e., POMA-T).
- c) The Short Physical Performance Battery test (i.e., SPPB; Guralnik et al., 1994) to evaluate the time spent to complete three balance tasks (i.e., SPPB-B), walk 4 meters at a comfortable speed (i.e., SPPB-G), and sit-to-stand 5 times from a chair (i.e., SPPB- ChS).
- d) Chair Sit-and-Reach Test (CSR; Jones et al., 1998) to measure lower body flexibility.

Ethics

All subjects are informed in advance about the study to obtain written informed consent to participate in the study, either directly or through their legal representatives. The present study was carried out following the process approved by the Autonomic Research Ethics of Galicia Committee, Spain (code 2018/010), and in agreement with the Declaration of Helsinki.

Data management and statistical analysis

The data of the participants are coded/pseudo-anonymized to ensure confidentiality and users' privacy for research use. Identifiable information is coded with artificial identifiers. The documentation to re-identify the participants will be only available to a medical doctor that collaborates with the research group, ensuring privacy during all data exploitation and dissemination (conferences, Ph.D. thesis, and scientific articles).

Data analysis will be made with the statistical programs SPSS, RStudio software package (Version 1.3.1093) and JAMOVI (The jamovi project, 2020, Version 1.2).

Data will be presented as the median and interquartile range for ordinal variables and the estimated marginal mean \pm standard deviation (SD) for continuous variables. The effect of the intervention will be analyzed employing nparLD (robust rank-based analysis of longitudinal data in factorial experiments) from the RStudio software package for nonparametric variables. Changes within and between groups will be analyzed by employing mixed models for repeated measures designs with the module GAMLj, which uses the R formulation of random effects as implemented by the lme4 R package in Jamovi software. The mixed models are a modern class of statistical models that extend regular regression models by including random effects parameters to account for dependencies among related data. We have chosen mixed models analysis as we expect a within-subject dependency in the variables measured before and after the intervention. Compared to traditional analyses that ignore these dependencies, mixed models provide more accurate (and generalizable) estimates of the effects, improved statistical power, and non-inflated Type I errors.

Duration of the project

	2019					2020	2021
	Jan-Aug	Sept	Oct	Nov	Dec	Jan-Dec	Jan-Dec
1. Project preparation and methodology							
2. Recruitment							
3. Baseline assessment							
4. Intervention (6 weeks per user)							
5. Post-intervention assessment							
6. Data analysis							
7. Dissemination							

References

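### Stratified blocks on three factors do not secure 12 per arm with 24 participants, and the planned mixed model does not adjust for the imbalance that can remain

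*SAP*

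**What the plan says.** The randomization text is in the SAP under Study setting and participants. The size and split are stated as "24 participants will be recruited and randomly placed into two groups: the exercise group (EG, n=12) and the control group (CG, n=12", and the allocation method as "A stratified permuted block randomization is employed that accounted for the GDS score, sex, and type of institutionalization".

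The inclusion criteria in the same section fix the possible levels of each factor:

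- GDS: "a score < 5 in the Global Deterioration Scale", described as running "from no cognitive decline to moderate cognitive decline"
- Sex: "men and women aged 65 and older"
- Care setting: "daycare patients or nursing home residents"

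The section does not say how GDS was grouped for stratification, what block size was used, or whether anything held the overall split at 12:12. Under Data management and statistical analysis, the comparison is described as follows: "Changes within and between groups will be analyzed by employing mixed models for repeated measures designs with the module GAMLj". That section names none of the three stratification factors as a model term.

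**The concern.** A permuted block equalises the arms only once it is complete. When 24 people are spread over many cells, many blocks stay open, and a person alone in a cell is in effect assigned by a coin toss. Two consequences follow. First, the stated 12 per arm is not something the described scheme secures. Second, the stratification may give little of the balance it was introduced to provide.

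The second matters more. With about 12 people per arm, a difference of two or more in the number of women, or of nursing home residents, is a noticeable share of the arm. If such a factor predicts change in body composition or function, the imbalance feeds into the estimated effect. The usual safeguard is to analyse by the factors used in randomization, and the mixed model as described does not include them.

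**Working it through.** **Inputs from the SAP.** N = 24, split 12:12; three factors; two sexes; two care settings; GDS below 5. The only arithmetic check on the stated sizes is 12 + 12 = 24, which holds.

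**Assumptions, because the SAP is silent.** GDS takes whole scores from 1, so four levels if used as scored, or two groups as the alternative. Block size is 2, 4 or 6. Participants are allocated one at a time. The factors are independent, in either an even mix or a skewed mix (GDS 10/20/30/40%, or 35/65% when grouped; sex 70/30; setting 60/40).

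**Cells.** GDS as scored: 4 x 2 x 2 = 16, and 24/16 = 1.5 per cell. GDS in two groups: 2 x 2 x 2 = 8, and 24/8 = 3 per cell.

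**Simulation, 20,000 trials per row.** Differences are mean absolute differences between arms in the number of participants in one category, for the even mix. In that mix sex and care setting behave alike, since each has two equally likely levels.

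| Scheme | Exactly 12:12, even / skewed | 10:14 or worse (even) | Sex difference | Difference per GDS score |
|---|---|---|---|---|
| 16 cells, blocks of 2 | 28% / 30% | 27% | 1.54 | 1.07 |
| 16 cells, blocks of 4 | 22% / 24% | 41% | 2.04 | 1.42 |
| 16 cells, blocks of 6 | 19% / 21% | 46% | 2.31 | 1.61 |
| 8 cells, blocks of 2 | 39% / 40% | 12% | 1.09 | not comparable |
| 8 cells, blocks of 4 | 30% / 31% | 24% | 1.45 | not comparable |
| 8 cells, blocks of 6 | 25% / 26% | 35% | 1.84 | not comparable |
| Unstratified blocks of 4 | 100% | 0% | 1.94 | 1.67 |
| Simple randomization | 16% | 54% | 2.75 | 1.92 |

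Repeat simulations move the 12:12 percentages by about one point.

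**Open blocks, 16 cells, even mix.** About 12.6 cells are occupied and 5.4 hold one person. Blocks opened but not filled: 7.7 of 15.8 (49%) for blocks of 2, 11.9 of 12.8 (93%) for blocks of 4, and practically all for blocks of 6.

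**Skewed mix, 16 cells.** The sex difference is 1.53, 1.98 and 2.36 for blocks of 2, 4 and 6, against 1.75 for an unstratified 12:12 list. For care setting it is 1.50, 1.91 and 2.23, against 1.89.

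**Precision cost of unequal arms.** Relative variance of a mean difference = (1/a + 1/b) / (1/12 + 1/12).

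- 11:13: 0.16783 / 0.16667 = 1.007, a cost of 0.7%
- 10:14: 0.17143 / 0.16667 = 1.029, a cost of 2.9%
- 9:15: 0.17778 / 0.16667 = 1.067, a cost of 6.7%

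**Why a main effect would not help.** With complete pre and post data, the group-by-time contrast is the difference between arms in mean change. A factor that is constant over time and enters only as a main effect adds the same amount to a participant's pre and post values, so it cancels from the change. It affects the contrast only as a factor-by-time term, or as a covariate when the post value is the outcome.

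**The case against.** Several objections have force.

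- **The number of strata is inferred.** A reader might infer that the SAP prescribes 16 strata. It does not, because no GDS grouping is given. With 8 cells, sex is balanced better than by the unstratified list at every block size tested in the even mix (1.09 to 1.84 against 1.94). The balance criticism therefore rests on GDS being used as scored; the 12:12 criticism does not.
- **The stratification is not useless.** A reader might infer that blocks hardly ever fill and that balance is lost throughout. With blocks of 2, about half fill, and all three factors are balanced better than by the list. With blocks of 4 or 6, GDS is still somewhat better balanced (1.42 and 1.61 against 1.67). Every stratified scheme with 16 cells beats simple randomization.
- **The arms may in fact have been 12 and 12.** A reader might infer that the stated group sizes are false. The trial ran from September to December 2019 and the document is dated April 2021, so the figures may describe what happened. The SAP also does not say that allocation was sequential. If a complete list was allocated after enrolment, 12:12 could have been arranged.
- **Materiality.** The precision cost is small, and an analysis of change largely absorbs differences in baseline level. Only imbalance in factors that predict change matters, and the SAP gives no figures from which a resulting bias could be calculated.
- **Minimisation is not a clean winner.** With two GDS groups it gave exactly 12:12 in 56 to 80% of trials, depending on the biased coin (0.8 or 0.9) and how imbalance was measured. Part of its gain over 16 cells comes from coarsening GDS.

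What remains is that the scheme as described does not secure the split stated beside it, under any block size or grouping tested, and that the mixed model leaves out the factors.

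**Conclusion.** The point holds in limited form. Under one-by-one allocation, exactly 12:12 occurs in about 20 to 30% of trials with 16 cells and about 25 to 40% with 8. If GDS is used as scored and blocks are of 4 or 6, sex and care setting are balanced no better than by an unstratified 12:12 list, while GDS is balanced somewhat better. With blocks of 2 the stratification works on all three factors.

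Loss of precision is a minor matter. The substantive gap is that imbalance in the factors can remain, the SAP gives too little detail to judge how much, and the mixed model as written does not adjust for it. These conclusions depend on the assumed factor mixes, block sizes and sequential allocation. They say nothing about the arm or cell counts actually obtained.

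**What to change.** **Now that allocation has taken place:**

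1. Report the GDS grouping, the block size, whether allocation was sequential, and the actual counts by cell and by arm.
2. Include sex, care setting and GDS (1-2 versus 3-4) in the between-group comparison, either as factor-by-time terms in the mixed model or as covariates in a model for the post-intervention value. Main effects alone are not enough.

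The cost is a few sentences and three extra parameters, one per two-level factor. In a comparison of change, residual degrees of freedom fall from 24 - 2 = 22 to 22 - 3 = 19. That is a real price with 24 participants and the reason to keep GDS in two groups. For outcomes sent to the rank-based analysis, the counts by arm and factor should at least be shown.

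**For the design text, or a successor trial:** use fewer strata, for example two GDS groups with blocks of 2 (mean sex difference about 1.1), or minimisation on the same three factors, and describe the split as approximately 12 per arm. This needs no extra participants. The downside is coarser control of individual GDS scores: two-group minimisation left a mean difference of 1.42 to 1.49 per score, against 1.07 for 16 cells with blocks of 2. Minimisation also needs software rather than a prepared list.

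### The only adverse-event method described is vital-sign monitoring at exercise sessions, so events that leave the readings normal, events between sessions and all control-group events would go uncounted

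*SAP*

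**What the plan says.** The SAP deals with adverse events in two places, both under the second Intervention heading, which follows Familiarization. The first states that "Control of adverse events was measured through the assessment and monitoring of vital signs" and gives the timing as "before, during (within the first 10 minutes), and after the intervention sessions". The signs listed are heart rate, systolic and diastolic blood pressure, and oxygen saturation. The second is narrower and leaves saturation out: "participants are monitored physiologically during each session (heart rate and blood pressure) to control any possible adverse effects".

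The same section says who has sessions: "The exercise group is requested to accomplish 18 sessions on the MOTomed Muvi". No session or equivalent contact is described for controls.

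What the two groups share is the pre/post assessment: "Participants (experimental and control group) are evaluated to examine the changes in body composition, functional performance, and resting cardiovascular state". The Measures section fills this in with bioimpedance and waist circumference, resting hemodynamics, frailty, POMA, SPPB and the chair sit-and-reach test.

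Symptoms during exercise appear once, under Familiarization, where "leg tightness/pain, dizziness, chest tightness/pain" are reasons for stopping the incremental test. They are not described as events to be recorded. Data management and statistical analysis plans nparLD and mixed models for the repeated measures, and no summary of adverse events.

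**The concern.** The described method is narrow in what it can detect, and it operates in one arm only. A participant with knee pain, dizziness or a fall whose readings are normal would not register. An event on a non-training day would not register. No event in a control would register.

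The participants are daycare users or nursing-home residents aged 65 or over, and the title and objective describe them as having multimorbidity. Some falls, complaints and acute illness are therefore plausible over six weeks whether or not anyone trains. Without a control count, a low number in the exercise group cannot be called reassuring, and a high number cannot be separated from background. Randomisation would protect the efficacy comparison, but the harms data would have no counterpart in the control group. The Introduction justifies physical activity partly by its few adverse effects relative to drugs, so a statement that no adverse events occurred would carry weight with readers.

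**Working it through.** The document states no event rate, no threshold for calling a reading an event and no expected count, so there is no figure to reproduce. The check sets the sections side by side and then sizes the gap on stated assumptions.

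1. **Content.** The method covers heart rate, blood pressure and saturation (Intervention). The symptoms that the document itself foresees on this device are leg, chest and dizziness symptoms (Familiarization). A symptom can occur with all three readings normal, and nothing in the Intervention section then makes it an event.

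2. **Window.** A session is 10 minutes of cycling, 5 of rest and 10 of cycling (Intervention). The one timed in-session reading falls in the first 10 minutes, so no reading is specified for the second bout until the session ends. Nothing is specified between sessions.

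3. **Arm.** Planned occasions for ascertaining events:
   - exercise group: 12 participants × 18 sessions = 216
   - control group: 12 participants × 0 sessions = 0

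4. **Shared data.** Both groups have resting heart rate, saturation and blood pressure before and after (Measures). These are outcomes at two time points. They can be compared between groups, but they do not record whether a fall, injury, illness or transfer happened in between.

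5. **Size of the control-arm gap, on assumed risks.** Let p be the per-person risk of at least one event from baseline to post-assessment.
   - Expected controls with an event = 12p: 12 × 0.10 = 1.2; 12 × 0.30 = 3.6.
   - Chance that at least one control has an event = 1 − (1 − p)^12: 46% at p = 5%, 72% at p = 10%, 93% at p = 20%.

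   The number recorded by the described method is 0 in every case.

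6. **What a two-arm table could support.** Against 0 of 12 in one group, the two-sided Fisher p-value for k of 12 in the other is 2 × C(12,k) / C(24,k).
   - k = 4: 2 × 495 / 10,626 = 0.093
   - k = 5: 2 × 792 / 42,504 = 0.037

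   Significance at 5% therefore needs at least 5 against 0. The exact power of the test is 9% for assumed risks of 10% and 30%, and 42% for 10% and 50%. The table should be descriptive.

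**The case against.** The strongest reply is that the two sentences describe bedside surveillance by a nurse and a doctor, not a definition of an adverse event. The document never says that other events are ignored, and event definitions often sit in a protocol. This stands in part: exclusivity is inferred from the absence of any other method, and a separate procedure that is not shown cannot be ruled out. It does not dispose of the point. The document is headed as both study protocol and statistical analysis plan, and it states a method for adverse events itself. The method it states is one-armed and narrow.

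Several stronger readings are tempting and should not be drawn:

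- A reader might infer that harms cannot be compared at all. The document does not support that: resting hemodynamics exist in both groups, and a medical register exists from which events might still be recovered.
- A reader might take the exclusion criteria, such as "physical limitations or musculoskeletal injuries that could affect cycling training performance", as a list of harms expected from training. They are screening rules.
- A reader might call the sample frail. Frailty is measured here; it is not an entry criterion.
- A reader might cite the wide confidence limit around 0 events in 12 as evidence of the defect. That width comes from 12 per group and would be the same under full ascertainment.
- A reader might cite session time as a share of all hours in six weeks. That does not say how many events are missed.

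It is also fair to say that the Objectives claim no harms comparison, and that 12 per group could not test one. That limits the remedy to a table and a caveat.

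**Conclusion.** The point holds. As written, adverse events are ascertained at up to 18 sessions per exercise participant and at none for controls, through readings that do not count symptoms, injuries, falls or illness when those readings are normal. A report of few or no adverse events from this method could not be interpreted against the control group. On assumed risks of 10% to 30%, that means 1.2 to 3.6 expected controls with an uncounted event; the assumed risks are not from the document. The conclusion rests on no other safety procedure having been in force beyond what the document describes. It does not affect the efficacy analyses. It should be corrected because the correction is cheap and because, without it, no safety statement beyond in-session vital signs is supported.

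**What to change.** Fix the event list and the window before looking at the records. For all 24 participants, from baseline to post-assessment, extract falls, musculoskeletal complaints, acute illness, hospital transfers and deaths, in the same way in both groups. The source is the medical register that the Exclusion criteria already use to verify contraindications. The collaborating doctor who holds the re-identification documentation (Data management and statistical analysis) can link the records. Tabulate participants with at least one event by randomised group, as counts with exact intervals and without a test.

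Report any session symptoms or early stops that were recorded, labelled as exercise-group-only data. A prospective session checklist is no longer an option: the study ran from September to December 2019 and the document is dated April 2021.

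State how complete the register is, especially for daycare users, whose events at home may not reach it; a blank entry should not be read as no event. If the extraction is not possible, state that harms were not ascertained in controls or outside sessions, and draw no comparative safety conclusion.

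The cost is one register extraction for 24 people at one site and one descriptive table. The downsides are a possibly less favourable event count and likely under-recording for daycare users.
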